## 8. OUTPUT PRESENTATIONS

The tables, listings and figures (TLFs) shells provided with this SAP describe the presentations for the double-blind portion (Part A) of this study and therefore the format and content of the summary TLFs to be provided by IQVIA Biostatistics.

Continuous variables will be summarized using descriptive statistics (number of subjects [n], mean, standard deviation [SD], median, minimum, and maximum, unless otherwise stated). The minimum and maximum will be reported to the same number of decimal places as the raw data recorded in the database. The mean and median will be reported to one more decimal place than the raw data recorded in the database. The SD will be reported to two more decimal places than the raw data recorded in the database.

Categorical variables will be summarized using frequency counts and percentages. Unless otherwise stated, the calculation of percentage will be based on the number of patients in the analysis set of interest.

P-values will be presented to three decimal places. P-values less than 0.001 will be presented as "<0.001".

Confidence intervals (CIs) will be presented to two more decimal places than the raw data.

Source data for summary tables and statistical analyses will be presented as patient data listings.

## 9. DISPOSITION AND WITHDRAWALS

Subject disposition and withdrawals, will be presented for the ENR Set.

Subject disposition and withdrawals will be presented by treatment group, when applicable, and overall. The number and percentage of subjects who were screened, screen failed, randomized, completed or discontinued the 6-week On-Treatment Period, reasons for early treatment discontinuation, completed or withdrew from Part A of the study, and reasons for study withdrawal will be presented. For subjects who completed the Part A treatment period, the number who enter safety follow-up, the number who enter Part B, and the number who directly roll over to Part B will be summarized. The reasons for treatment discontinuation will also be presented by treatment group and by time to treatment discontinuation, categorized based on the planned visits ( $\leq$  Day 8,  $>$  Day 8 to  $\leq$  Day 15,  $>$  Day 15 to  $\leq$  Day 22,  $>$  Day 22 to  $\leq$  Day 29,  $>$  Day 29 to  $\leq$  Day 36,  $>$  Day 36 to  $\leq$  Day 43). The reasons for study withdrawal are listed in [Table B](#). The same reasons apply to treatment discontinuation except for lost to follow-up

and screen failure.

A subject is defined to have completed the Part A treatment period if the subject has completed the 6-week On-Treatment Period and procedures.

A subject is defined to have completed Part A of the study if the subject has completed the 6-week On-Treatment Period and the End-of-Study assessments on Study Day 57 ( $\pm 2$ ) or directly rolled over to Part B.

**Table B: Reasons for Study Withdrawal and Study Medication Discontinuation Terminology**

[figure not shown]
[figure not shown]
eCRF Terminology
Adverse event
Adverse event associated with worsening of bipolar depression
Adverse event not associated with worsening of bipolar depression
Death
Lack of efficacy
Lost to follow-up
Protocol violation
Physician decision
Screen Failure
Study terminated by sponsor
Subject withdrew consent:
Personal or family reasons
Refused to provide a reason and refused or End of study procedures
Self-reported adverse event
Self-reported lack of efficacy
Other

Adverse event preferred terms associated with worsening of bipolar depression will be

identified by the Medical Monitor review prior to database lock. The number and percentage of randomized subjects who discontinued due to an adverse event associated with worsening of bipolar depression will be summarized. The number and percentage of randomized subjects discontinued due to an adverse event not associated with worsening of bipolar depression will also be presented.

The time to treatment discontinuation due to all reasons, adverse events, lack of efficacy, or due to any other reason of special interest will be evaluated separately using the Kaplan-Meier method. Time to treatment discontinuation will be defined in days for those subjects who are randomized and receive at least one dose of study medication but discontinue study medication prior to Day 43 as the date of discontinuation minus date of first dose of study medication plus 1. Subjects who complete the On-Treatment Period or who discontinue for a reason other than the one being evaluated will be censored. The Log-rank test will be used to compare the time to discontinuation between each treatment group and the placebo group. The same analysis will be repeated for time to treatment discontinuation for any reason, where only subjects who complete the On-Treatment Period will be censored.

The number of subjects randomized by site will be summarized by treatment group and overall for all randomized subjects.

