7.2 Sample Size Calculations

In Part A, approximately 549 patients will be randomly assigned in a 1:1:1 ratio to 1 of the 3 treatment arms, which will provide approximately 471 evaluable patients, assuming an approximate 14% early discontinuation rate before a post-dose assessment in the primary efficacy endpoint (MADRS). A sample size of 471 patients (157/arm) will provide at least 90% power to detect a clinically relevant treatment difference from placebo of 3 points on the MADRS total score within each ITI-007 dose level, with a common standard deviation of 7.5

at an overall 2-sided significance level of 0.05. It was not possible to apply the proposed Hommel procedure for multiplicity adjustments (for comparing 2 doses of ITI-007 to placebo) to the sample size calculation; therefore, the sample size calculation used a more conservative Bonferroni adjustment. The study therefore has at least 90% power to detect the previously mentioned clinically relevant treatment difference within each ITI-007 dose. The sample size calculation was performed using PASS software version 12.

In Part B, up to approximately 549 patients will be enrolled. The sample size is not based on statistical considerations, rather on the number of patients who may be eligible based on participation in Part A of the study. It is estimated that the majority of patients will continue treatment for the full 6 months.

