7.5.1 Patient Disposition, Analysis of Demographics and Other Baseline Characteristics

Patient disposition will be summarized for each Part by treatment group, when applicable, and overall, including incidence of screen failure, and treatment or study discontinuation and the corresponding reasons. The number and percentage of randomized patients who discontinued due to an adverse event associated with worsening of bipolar depression will be

summarized. Similarly, the number and percentage of randomized patients who discontinued due to an adverse event not associated with worsening of bipolar depression will also be presented. Time to treatment discontinuation due to all reasons, adverse events, lack of efficacy, or due to any other reason of special interest will be evaluated separately using the Kaplan-Meier method, where patients who complete the On-Treatment Period or who discontinue for a reason other than the one being evaluated will be censored. The Log-rank test will be used to compare the time to discontinuation between each treatment group and the placebo group (Part A).

Demographic and baseline characteristics, including bipolar disorder diagnosis and bipolar disorder baseline efficacy measures, will be summarized for each part by treatment group for Part A only using descriptive statistics. No inferential statistics will be presented.

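### Reason-specific discontinuation is estimated by Kaplan-Meier with other reasons censored; read as a probability of stopping for that reason, the curve is biased upward

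*SAP*

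**What the plan says.** SAP section 9, in the text after Table B, plans separate analyses of time to treatment discontinuation for adverse events, "lack of efficacy, or due to any other reason of special interest will be evaluated separately using the Kaplan-Meier method". The censoring rule is "Subjects who complete the On-Treatment Period or who discontinue for a reason other than the one being evaluated will be censored". The between-arm comparison follows: "The Log-rank test will be used to compare the time to discontinuation between each treatment group and the placebo group".

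Protocol section 7.5.1 has the same rule, censoring patients "who discontinue for a reason other than the one being evaluated will be censored", and the statistical methods part of the Protocol Synopsis repeats it. No readable text in either document plans a cumulative incidence function or any other competing-risks estimate.

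Three other planned outputs bear on the point:

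- The SAP repeats the analysis for discontinuation for any reason, "where only subjects who complete the On-Treatment Period will be censored".
- SAP section 9 tabulates stops by reason: "The reasons for treatment discontinuation will also be presented by treatment group and by time to treatment discontinuation", in six visit intervals. It also counts discontinuations due to adverse events associated and not associated with worsening of bipolar depression.
- SAP section 16.1.1 gives frequencies and percentages of adverse events leading to study withdrawal or discontinuation of study medication.

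**The concern.** Censoring is harmless to Kaplan-Meier when a censored subject could still have the event later, at the same rate as those who remain. Someone who has already stopped treatment for lack of efficacy cannot afterwards stop it for an adverse event. Treating that person as censored makes the adverse-event curve describe a setting in which no other reason for stopping exists.

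Here nearly all early censoring is of this kind. Treatment lasts a fixed 6 weeks, and SAP section 9 removes loss to follow-up from the list of treatment-discontinuation reasons. Apart from termination by the sponsor, or subjects still on treatment at an interim look, a subject censored before completion is one who stopped for a competing reason.

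At stake is how tolerability and lack-of-efficacy dropout are read from the curves. If the mix of reasons differs between an ITI-007 dose and placebo, the curve for one reason can shift between arms because of the other reasons.

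**Working it through.** **Plan figures.** The documents state no discontinuation probability by reason, so there is none to reproduce. The only dropout figure is in Protocol section 7.2, "assuming an approximate 14% early discontinuation rate before a post-dose assessment in the primary" efficacy endpoint. It serves to convert evaluable into randomized patients: 157 / 0.86 = 182.6, rounded up to 183 per arm, and 3 × 183 = 549, as stated. It concerns stops before a post-dose MADRS, so it is not a 6-week total.

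**Inputs (assumed).** T is the total proportion stopping during treatment, and s is the share of those stops due to the reason of interest. Cause-specific hazards are constant over the treatment period, with total cumulative hazard L = −ln(1 − T).

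**Formulas.**

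- Cumulative incidence for the reason: s × (1 − e^(−L)) = s × T.
- One minus Kaplan-Meier with other reasons censored: 1 − e^(−sL) = 1 − (1 − T)^s.

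Example, T = 25% and s = 0.25: the cumulative incidence is 0.25 × 0.25 = 6.25%, and one minus Kaplan-Meier is 1 − 0.75^0.25 = 6.94%.

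Each cell shows cumulative incidence / one minus Kaplan-Meier, with the excess in percentage points in brackets:

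| T | s = 0.10 | s = 0.25 | s = 0.50 | s = 0.75 |
|---|---|---|---|---|
| 10% | 1.00 / 1.05 (0.05) | 2.50 / 2.60 (0.10) | 5.00 / 5.13 (0.13) | 7.50 / 7.60 (0.10) |
| 14% | 1.40 / 1.50 (0.10) | 3.50 / 3.70 (0.20) | 7.00 / 7.26 (0.26) | 10.50 / 10.70 (0.20) |
| 25% | 2.50 / 2.84 (0.34) | 6.25 / 6.94 (0.69) | 12.50 / 13.40 (0.90) | 18.75 / 19.41 (0.66) |
| 40% | 4.00 / 4.98 (0.98) | 10.00 / 11.99 (1.99) | 20.00 / 22.54 (2.54) | 30.00 / 31.83 (1.83) |

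In relative terms the excess runs from about 1% (T = 10%, s = 0.75) to about 25% (T = 40%, s = 0.10). The 14% row is an arbitrary total that happens to share its number with the protocol's figure.

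**Simulation.** With 2000 runs at 183 per arm, T = 25% and s = 0.25, the means are 6.92% (one minus Kaplan-Meier) and 6.24% (cumulative incidence), in line with the formula.

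**Timing.** Constant hazards is itself an assumption. At T = 25% and s = 0.25, 6.25% stop for the reason of interest and 18.75% for others. If all other stops come first, one minus Kaplan-Meier is 6.25 / (100 − 18.75) = 7.69%. If they all come last it is 6.25%, with no excess.

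**Difference between arms.** Take a true incidence of 5% in both arms.

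- With 10% stopping for other reasons, T = 15% and s = 1/3: 1 − 0.85^(1/3) = 5.27%.
- With 25% stopping for other reasons, T = 30% and s = 1/6: 1 − 0.70^(1/6) = 5.77%.

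Half a point separates two arms whose true incidence is the same.

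**The case against.** The strongest case on the other side has four parts.

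1. **No stated misuse.** The SAP says the times will be evaluated by Kaplan-Meier and compared by log-rank. It does not say that one minus Kaplan-Meier will be tabulated as a risk. SAP section 8 leaves output content to table shells that are not among the documents. This stands: the error lies in reading the curve as a probability of stopping for the reason. The curves still invite that reading, and the readable text offers no alternative time-based estimate.

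2. **The right number is already planned.** When every dosed subject is followed to completion or to a stop, the count for a reason divided by the number dosed equals the Aalen-Johansen estimate at the end of treatment. The table by visit interval is a grouped form of the same curve. This also stands, and it takes away most of the practical weight.

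3. **The excess is small against sampling error.** With 183 per arm the standard error is √(p(1 − p)/183). At p = 12.5% it is 2.4 points, against an excess of 0.90. At p = 20% it is 3.0 points, against 2.54. The excess is below one standard error in every cell of the table. That limits its importance, but a systematic excess that can be removed at no cost need not be kept.

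4. **It is a disposition analysis.** Efficacy is in SAP section 15 and safety in section 16. This is correct.

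A reader might also infer that the reason-specific figures must sum to more than total discontinuation. That needs a curve for every reason: with T = 25% and three equal causes, 3 × (1 − 0.75^(1/3)) = 27.4%. The plan names only adverse events, lack of efficacy and unspecified reasons of special interest, while Table B lists many more. At T = 25% with a quarter share each, the two named curves sum to 6.94 + 6.94 = 13.9%, well under the total.

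**Conclusion.** The point holds as a free improvement of low severity. Reason-specific Kaplan-Meier with other reasons censored is never below the cumulative incidence, and it exceeds it once a competing stop precedes an event of interest. That direction needs no assumption about rates. The size does: the figures in the table rest on assumed totals, assumed shares and constant hazards, and depend on when the other stops occur.

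Two stronger readings are not supported. The log-rank comparison is not invalid: with other reasons censored it properly compares cause-specific hazards, though it does not test a difference in cumulative incidence. Nor does the issue reach the trial's conclusions: the all-cause curve has no competing reason, and the primary and key secondary analyses, the alpha and the sample size do not use these curves.

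**What to change.** In SAP section 9:

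- Present discontinuation for adverse events, lack of efficacy and any other reason of special interest with the Aalen-Johansen cumulative incidence function, by arm.
- Keep Kaplan-Meier for discontinuation for any reason.
- Keep the log-rank test, labelled as a comparison of cause-specific hazards, so that curve and p-value are not taken to describe the same quantity. Gray's test can be added if a test on the cumulative incidence scale is wanted.
- In the same edit, say whether the self-reported adverse event and self-reported lack of efficacy entries, listed under withdrawn consent in Table B, count as events for those two curves. The readable text does not say.

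Make the same change in Protocol section 7.5.1 and the Synopsis. Protocol section 7 allows changes of analysis method to be documented in the SAP without an amendment, so the SAP edit need not wait.

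The cost is a few lines of text and a small programming change. The stop dates and reason codes are already collected, and no sample size, alpha or visit schedule changes.

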## 11. DEMOGRAPHIC AND OTHER BASELINE CHARACTERISTICS

Demographic data and other baseline characteristics will be presented for the ITT Set, [REDACTED] and SAF Set.

No formal statistical testing will be carried out for comparing demographic or other baseline characteristics between treatment groups.

The following demographic and other baseline characteristics will be reported for this study:

## Demographics

- Age (years) calculated as (Date of Informed Consent – Date of Birth)/365.25;
- Gender;
- Race;
- Ethnicity;

## Other Baseline Characteristics

---

- Waist circumference (cm);
- Weight (kg);
- Height (cm);
- Body Mass Index (BMI) (kg/m^2), where BMI (kg/ m^2) = weight (kg) / height (m)

#### Consumption Habits

- Alcohol consumption;
- Caffeine consumption;
- Tobacco use;

#### Bipolar Disorder Diagnosis

- Bipolar disorder diagnosis (Bipolar I or II);
- Age at first diagnosis of Bipolar Disorder (years);
- Duration of current major depressive episode (weeks);
- Number of lifetime depressive episodes;
- Hospitalization for emotional or psychiatric problems;
- Number of hospitalizations in lifetime;
- Hospitalization in the past year;

#### Bipolar Disorder Baseline Efficacy

- Baseline efficacy parameters, including rater-administered MADRS total score, CGI-BP-S score, SDS total score, Q-LES-Q-SF, WHO-5 Well-being Index, and NEO-FFI;

#### Bipolar Disorder Baseline Safety

- Baseline safety parameters, including BARS total score, BARS global assessment of akathisia, SAS total score, AIMS total score, YMRS total score, and C-SSRS assessment of suicidal behavior and ideation;

## **12. MEDICAL HISTORY**

Medical History information will be presented for the SAF Set.

---

Medical History will be coded using Medical Dictionary for Regulatory Activities (MedDRA) central coding dictionary currently in effect at the time of interim analysis or final Part A database lock.

Medical History conditions are defined as those current and past conditions at Screening.

The number and percentage of subjects with at least one pre-existing condition as well as the number of subjects having pre-existing conditions will be summarized by system organ class (SOC), preferred term (PT), treatment group, and overall. Within each subject, multiple reports of pre-existing conditions that map to a common PT and SOC will be condensed into a single medical history for incidence counts.

### **13. PRIOR AND CONCOMITANT MEDICATIONS**

Medications will be presented for the SAF Set and coded to preferred names using Who Drug Dictionary.

See [Appendix 2](#) for handling of partial dates for medications, in the case where it is not possible to define a medication as prior, prior concomitant, concomitant, or post-treatment, the medication will be classified by the worst case, i.e. concomitant.

For Part A, a medication is considered to have started prior to the first dose of study medication if indicated to have started prior to the first dose of study medication on the eCRF. If the medication started prior to the first dose of study medication, it is considered to have ended prior to the first dose of study medication if indicated to have ended prior to the first dose of study medication on the eCRF.

A medication is considered to have started after the last dose of study medication if indicated as such on the eCRF, assuming it started after all study procedures and assessment related to the last dose of study medication.

- Part A 'Prior' medications are medications which started and stopped prior to the date of first dose of study medication.
- Part A 'Prior concomitant' medications are medications that started prior to and stopped after the first dose of study medication.
- Part A 'Concomitant' medications are medications that:
  - started on or after the date of first dose of study medication and started prior to the date of last dose of study medication,
  - AND stopped after the date of first dose of study medication or were ongoing at the completion of Day 43 post-dose assessments on Day 43 (or last treatment day for subjects who discontinue treatment), or after the last dose of study

medication (if planned assessments are not performed).

- Part A 'Post-treatment' medications are medications that started after completion of Day 43 (or last treatment day for subjects who discontinue treatment) assessments that are planned to be conducted after the last dose of study medication and before the start of Part B. Post-treatment medications will only be summarized for subjects not enrolling over into Part B study phase upon completing treatment in Part A.

Prior, prior concomitant, concomitant, and post-treatment medication use will be summarized separately by PT using frequencies and percentages by treatment group. Medications will be sorted alphabetically by PT in summaries. Subjects with multiple occurrences of a medication in the same PT will only be counted once within the PT for each summary.

During the study, a subject may be treated with zolpidem if taken no more than 3 times per week and only during the Screening Period and first 2 weeks of the On-Treatment Period. The number and percent of subjects in the ITT Set receiving zolpidem and the total number of days on zolpidem will be summarized by treatment group for the Screening Period, for each week on study treatment (Days 1-8, Days 9-15, Days 16-22, Days 23-29, Days 30-36 and Days 37-43), and for post treatment.

Other medications will be summarized by treatment group and study period if deemed necessary.

## **14. STUDY MEDICATION EXPOSURE AND TREATMENT COMPLIANCE**

Exposure to study medication and treatment compliance in Part A will be presented for the SAF Set and ITT Set.

The date of first and last study medication administration will be taken from the eCRF 'Dosing' form. If multiple entries occurred on this form, the earliest 'start date of study medication' and the latest 'stop date of study medication' will be used.

Duration of exposure (days) will be calculated as (date of last dose of study medication) – (date of first dose of study medication) + 1. Duration of exposure will be summarized by treatment group as a continuous variable, using mean, SD, median, minimum and maximum. In addition, the number and percentage of subjects within each planned Study Week (1-8 days, 9-15 days, 16-22 days, 23-29 days, 30-36 days, 37-43 days, and > 43 days), will be presented.

For each subject, dosing compliance (%) will be calculated as  $100 \times (\text{number of compliant days}) / (\text{number of days in the On-Treatment Period})$ . A day within the On-Treatment Period will be considered a compliant day if the subject had 2 capsules. The "Number of Days in the On-Treatment Period" is equivalent to the duration of exposure as defined above. The number and percentage of compliant and non-compliant subjects will be presented. Non-compliant subjects are defined as those subjects with a compliance less than 80% or greater than 120%.

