5.2 Treatments Administered

In Part A, patients will be assigned to receive either ITI-007 (40- or 60-mg doses) or placebo. Study center personnel will receive a treatment card number from the IVRS/IWRS for each patient at each clinic visit, to ensure that the correct investigational product is dispensed.

Patients will self-administer all doses orally, once daily, at home, in the evening for the duration of the on-treatment period. Treatment will be administered between 8:00 PM and 10:30 PM, at approximately the same time each day whenever possible. Treatments will be provided in dose cards containing 2 strips of over-encapsulated tablets (Section 5.4.1). Patients will be instructed to take 2 capsules (1 capsule from each strip) per dose.

In Part B, all patients will receive ITI-007 (60 mg). Patients will self-administer all doses orally, once daily, at home, in the evening for up to approximately 6 months (175 days) at approximately the same time each day whenever possible. Patients will be instructed to take 1 tablet per dose. (Section 5.3.2).

In Part B, a one-time dose reduction will be allowed for patients who (in the opinion of the investigator and as confirmed by the Medical Monitor) are not tolerating the 60 mg dosage. If the patient is not able to tolerate the 40 mg dose, they must be withdrawn from the study and undergo evaluations required in the early termination visit.

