5.3 Identity of Investigational Product

5.3.1 Investigational Product for Part A

ITI-007 will be supplied as 20- and 60-mg over-encapsulated tablets (capsules) (Table 5-1). The following drug supplies will be used in the study:

Table 5–1 **Table for Dosing Schedule**

| Study Drug | Dosing Schedule |
|---------------|---|
| 40-mg ITI-007 | 2 over-encapsulated tablets of 20-mg ITI-007 Daily Dose: 40-mg ITI-007 |
| 60-mg ITI-007 | 2 over-encapsulated tablets: 1 over-encapsulated tablet of 60-mg ITI-007 and 1 over-encapsulated tablet of placebo Daily Dose: 60-mg ITI-007 |
| Placebo | 2 over-encapsulated tablets of placebo Daily Dose: 0-mg ITI-007 |

Each ITI-007 dosing container will be labeled according to local laws and regulations.

The composition of the over-encapsulated tablets is listed in Table 5-2.

[figure not shown]
Table 5–2 Dosage Composition for Part A

Over-encapsulated placebo tablets are identical in appearance to ITI-007 and have the same excipient ingredients as ITI-007 but do not have the active compound.

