5.4 Management of Clinical Supplies

5.4.1 Study Drug Packaging and Storage

In Part A, ITI-007 and matching placebo will be prepared according to current Good Manufacturing Practice standards in carded blister strips and shipped under ambient conditions by Catalent, on behalf of ITI. Each treatment card will contain a sufficient quantity for 1 patient for each week (7 doses, plus 1 extra) of the 6-week treatment period, to be distributed at weekly visits. Each ITI-007 dosing container will be labeled according to local laws and regulations.

The dose card for each study treatment will contain two 1×8 strips of over-encapsulated tablets (final product in capsule form) as described in Table 5–3.

Table 5–3 **Part A Weekly Treatment Cards**

| Treatment | Card Contents |
|---------------|--|
| Placebo | Two 1×8 strips of placebo over-encapsulated tablets (8 over-encapsulated tablets/strip) |
| 60-mg ITI-007 | One 1×8 strip of 60-mg ITI-007 over-encapsulated tablets (8 over-encapsulated tablets/strip); One 1x8 strip of placebo over-encapsulated tablets (8 over-encapsulated tablets /strip) |
| 40-mg ITI-007 | Two 1×8 strips of 20-mg ITI-007 over-encapsulated tablets (8 over-encapsulated tablets /strip) |

Note: Each card will hold 16 over-encapsulated tablets in 2 strips of 8.

Study drug must be stored in a secure area (e.g., a locked cabinet) while in storage at the study site, protected from moisture, and kept at a room temperature between 15°C and 30°C (59°F-86°F). Patients will be instructed to store the weekly treatment card at room temperature at home, out of the reach of children. Patients will be instructed to take 2 capsules, 1 capsule from each strip per dose for Part A.

In Part B, ITI-007 will be provided to the study site by Catalent on behalf of ITI. Each treatment card will provide sufficient quantity for 1 patient for 4 weeks (28 doses). At the Part B, enrollment visit (Visit 8 of Part A), the patient will receive treatment cards containing sufficient quantities for 4 weeks. Each ITI-007 dosing container will be labeled according to local laws and regulations.

The treatment card for each study treatment is presented in Table 5-5.

Table 5-4 Part B Treatment Cards for 4 Weeks of Treatment

| Treatment | Card Contents |
|---------------|--|
| 60 mg ITI-007 | Two 2 × 7 strips of 60 mg ITI-007 tablets (14 tablets/strip) |

Note: Each treatment card will hold 28 tablets each.

| Treatment | Card Contents |

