5.5.2 Medication Errors

Dispensing study treatment to be taken by patients in an outpatient study increases risk for medication errors. All errors in medication dispensing or administration must be carefully documented. These errors may include but are not limited to providing the wrong dose (in Part A, not taking 2 capsules per dose or taking too many capsules per dose; in Part B, taking more than 1 tablet per dose), losing medication, or administration at the wrong time of day. Medication adherence will be emphasized at every visit. Written instructions will be provided to the patients with the weekly medication card in order to minimize medication error. Additional adherence procedures may be implemented.

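### SAP 14 scores compliance by capsule number alone, so in the 60 mg arm a day at 120 mg or 0 mg can count as compliant

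*SAP*

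**What the plan says.** - **SAP 14** computes compliance as 100 × compliant days / days in the on-treatment period, and equates that denominator with duration of exposure. The numerator rule is "A day within the On-Treatment Period will be considered a compliant day if the subject had 2 capsules". It sets no condition on which strip the capsules came from. Subjects below 80% or above 120% are classed as non-compliant.
- **Protocol 5.2** gives the dosing instruction: "Patients will be instructed to take 2 capsules (1 capsule from each strip) per dose". Protocol 5.4.1 repeats it.
- **Protocol 5.3.1, Table 5-1**, gives the 60 mg dose as "2 over-encapsulated tablets: 1 over-encapsulated tablet of 60-mg ITI-007 and 1 over-encapsulated tablet of placebo Daily Dose: 60-mg ITI-007".
- **Protocol 5.4.1, Table 5-3**, puts those two components on separate strips of 8. The 40 mg card has two strips of 20 mg capsules, and the placebo card has two strips of placebo. Each weekly card covers 7 doses plus 1 spare.
- **Protocol 5.7** assesses compliance by counting unused capsules at each visit. No visible text says that the count is kept by strip.
- **Protocol 5.5.2** illustrates a wrong dose in Part A by number: "not taking 2 capsules per dose or taking too many capsules per dose". The list is expressly open-ended.

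**The concern.** The protocol's dose definition has two parts: two capsules, and one from each strip. SAP 14 keeps only the first part. In two arms this makes no difference to the dose. In the 60 mg arm the strip decides whether the patient receives the assigned dose, twice that dose, or none.

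The compliance table will be read as evidence that patients took the dose to which they were assigned. For the 40 mg and placebo arms a two-capsule day supports that reading. For the 60 mg arm it does not, so the same percentage means something different across columns of one table. The total count of returned capsules cannot correct this, because a patient who uses the strips wrongly can return the same number of capsules as one who uses them correctly.

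**Working it through.** **Inputs.** Capsule strengths come from Tables 5-1 and 5-3. Card stock is 8 + 8 = 16 capsules for 7 doses plus 1 spare (protocol 5.4.1). The compliance formula is from SAP 14.

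**Step 1: dose on a two-capsule day** (sum of the two strengths). The one-from-each column reproduces the daily doses in Table 5-1.

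| Arm | One from each strip | Two from strip 1 | Two from strip 2 | SAP 14 score |
|---|---|---|---|---|
| 60 mg | 60 + 0 = 60 mg | 60 + 60 = 120 mg | 0 + 0 = 0 mg | compliant in all three |
| 40 mg | 20 + 20 = 40 mg | 40 mg | 40 mg | compliant in all three |
| Placebo | 0 mg | 0 mg | 0 mg | compliant in all three |

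Only the 60 mg arm can have a compliant day at a dose other than the assigned one.

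**Step 2: what card stock allows in a week.** Let x be days with two active capsules, y days with two placebo capsules and w days with one of each. Then x + y + w = 7, 2x + w ≤ 8 and 2y + w ≤ 8. With w = 0, the only solutions are (x, y) = (4, 3) and (3, 4). This is a patient who empties one strip before starting the other.

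| 60 mg card, 7 days | Days at 120 / 0 / 60 mg | Used, active + placebo | Returned, active + placebo | Weekly dose |
|---|---|---|---|---|
| Correct use | 0 / 0 / 7 | 7 + 7 = 14 | 1 + 1 = 2 | 7 × 60 = 420 mg |
| Active strip first | 4 / 3 / 0 | 8 + 6 = 14 | 0 + 2 = 2 | 8 × 60 = 480 mg |
| Placebo strip first | 3 / 4 / 0 | 6 + 8 = 14 | 2 + 0 = 2 | 6 × 60 = 360 mg |

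All three rows return 2 of 16 capsules.

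**Step 3: compliance over 42 days in this extreme case.** The SAP rule gives 42/42 = 100%. A rule of one from each strip gives 0/42 = 0%. Under the strip rule, 8 wrong-strip days give 34/42 = 81.0% and 9 give 33/42 = 78.6%, so the 80% limit is crossed at 9 days.

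**Step 4: the upper limit.** Each day adds 0 or 1 to the numerator and 1 to the denominator, so the formula cannot exceed 100%. The 120% limit can never be reached and cannot flag double-dose days.

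**Step 5: what a count by strip would show.** When every day has two capsules, active used minus placebo used = (2x + w) − (2y + w) = 2(x − y). The count therefore shows net imbalance only.
- (x, y, w) = (4, 3, 0) returns 0 + 2 and is flagged.
- (1, 0, 6), a single slip, also returns 0 + 2. A flag does not give the number of wrong days.
- (3, 3, 1) uses 7 + 7 and returns 1 + 1. Six of seven days are wrong and nothing is flagged.

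**The case against.** The case against is strong on impact, and most of it stands.

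A reader might infer that double doses in the 60 mg arm go unrecognised as overdoses. The documents do not support that. Protocol 5.5 treats any dose above the protocol dose as an overdose to be reported promptly, and 5.5.2 requires all administration errors to be documented under an open list. A wrong-strip dose that comes to light is already covered. The gap lies in the compliance variable, which does not use those records.

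A reader might also infer that a missed dose scores as compliant. A day with no capsules is still non-compliant; only two capsules from the placebo strip give a compliant day at 0 mg.

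Nor can it be said that the efficacy or safety conclusions rest on these figures. The planned contrasts in SAP 15.1.3 are each dose against placebo, the ITT Set in SAP 6.3 groups subjects as randomized, and no visible model uses compliance. Table 6-5 of the protocol also schedules PK samples on Days 8, 22 and 43, a sparse but separate view of exposure.

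The error requires a patient to depart from a clear instruction, and protocol 5.5.2 provides written instructions with each weekly card. The one-strip-first week is a constructed extreme. The schedule of events and the dosing and accountability forms are not available, so counts by strip may already exist.

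Finally, a strip rule has a fault of its own: in the 40 mg and placebo arms it marks as non-compliant some days on which the assigned dose was taken.

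None of this removes the mismatch between SAP 14 and the protocol's definition of a dose.

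**Conclusion.** The point holds as a measurement fault in one descriptive variable. In the 60 mg arm only, SAP 14 can report up to 100% compliance for a patient with no day at the assigned dose, and neither a total capsule count nor the 120% limit would show it.

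The size of the effect across the trial is unknown, because the documents give no frequency for wrong-strip use. The 0% against 100% contrast is the bound set by card stock, not an expected value. The result assumes that the SAP variable is built as written, without strip information from a form that is not visible.

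The ITT primary analysis is unaffected. Any role in the per-protocol set cannot be judged: protocol 7.3 leaves the major-deviation criteria to be finalized before analysis, and SAP 6.4 is blacked out. The change is worth making because it is cheap and aligns the SAP with the protocol.

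**What to change.** 1. In SAP 14, define a compliant day as one capsule from each strip, matching protocol 5.2 and 5.4.1.
2. Record the unused-capsule count already made at each visit separately for each strip.
3. Report, by arm, the weeks in which the two strips' used counts differ. Visit counts alone cannot give the number of wrong-strip days, so this weekly report carries the information where no daily record by strip exists.
4. If counts by strip were not collected, state in the SAP and the report that compliance in the 60 mg arm reflects capsule number, not dose delivered.

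**Cost.** One SAP sentence and one extra count field. The placebo capsules are identical in appearance to active (protocol 5.3.1) and the cards are identical (5.6), so counting by strip need not reveal assignment.

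**Downsides.** Reported compliance will be slightly lower, including for 40 mg and placebo patients whose dose was in fact correct. The measure is then adherence to the instruction, and delivered dose should be read by arm after unblinding. Errors that balance within a week stay undetected without a daily record by strip.

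How a wrong-strip dose is handled clinically is left to protocol 5.5 and 5.5.2 as they stand.
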